12.4.6 Protocol Deviations

Protocol deviations will **not** be collected for this study. A protocol deviation is an accidental or unintentional change to or non-compliance with the research protocol that does not increase risk or decrease benefit or does not have a significant effect on the subject's rights, safety or welfare, and/or on the integrity of the data. A deviation may be due to the research subject's non-adherence or an unintentional change to or non-compliance with the research protocol on the part of a researcher.

12.4.7 Protocol Violations

All protocol violations (i.e. any deviation from the protocol that may impact the subjects' rights, safety, or well-being, or the completeness, accuracy or reliability of the study data, or a deviation from FDA or IRB regulations or standards) shall be reported to Zimmer Biomet within 24 hours and to the reviewing IRB per policy. A Protocol Violation Form shall be completed that includes a full explanation of the event and outcome.

The Investigator will assist Zimmer Biomet in corresponding with the reviewing IRB, where appropriate, to determine the appropriate course of action.

12.4.8 Study Termination

Study subject participation is expected to end upon completion of the subject's two-year follow-up visit unless the subject voluntarily withdraws from the study, is withdrawn from the study by the Investigator, is lost to follow-up, undergoes revision to remove a study device, or expires. Reason(s) for study completion must be documented on the **Study Completion** case report form.

If the Sponsor decides to terminate the study early, the Sponsor will inform the Investigators of the reason for early study termination. It is the responsibility of the Investigators to inform their IRB or EC as applicable according to local and national laws/regulations.

12.4.9 Adverse Events

An adverse event (AE) is defined as an untoward medical occurrence, unintended disease or injury, or untoward clinical signs (or change or worsening of a pre-existing medical condition) in a patient, which may or may not have an association with the device or procedure. In addition an adverse device effect is defined as ‘any untoward and unintended response to a medical device’.

Each Adverse Event Form should only include one adverse event. When reporting an adverse event, it is important to record the diagnosis rather than the symptoms, event or treatment. For example, a subject who undergoes a Total Hip Arthroplasty after the Subchondroplasty Procedure may have had the procedure due to increased pain caused by hip osteoarthritis. In this case, ‘Severe Osteoarthritis’ or something similar (as determined by the Investigator) should be recorded as the diagnosis rather than ‘Total Hip Arthroplasty’. Abbreviations/colloquialisms should also be avoided when recording the diagnosis.

For this study, **only AEs which are possibly or definitely related to the device or procedure will be reported to the sponsor**. The determination whether the AE is related to the device or procedure will be based upon whether a causal relationship between the device or procedure and the AE is at least a reasonable possibility, i.e., the relationship cannot be ruled out. A causal relationship cannot be ruled out if, in the medical judgment of the Investigator, the effect follows a reasonable temporal association with the use of the device.

For this study, device implies the AccuFill Bone Substitute Material and procedure implies the Subchondroplasty Procedure.

13 Safety Management – Medical Events/Adverse Events

Adverse events are required to be reported on the **Adverse Event Report** case report form. The completed **Adverse Event Report** case report form must be submitted to the Sponsor in a timely manner. The Investigator or Designee will also promptly provide the Sponsor with any additional requested information required for the Sponsor to comply with regulatory requirements. If applicable per their reporting requirements, the Investigator or Designee will also report applicable adverse event(s) to their IRB or EC.

The following definitions are from ISO 14155:2020.

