7.1 Study Device

The Subchondroplasty Procedure targets and fills subchondral bone defects in the form of a cyst and/or bone marrow lesion (BML), insufficiency fracture or bone defect associated with early stage avascular osteonecrosis (AVN) with AccuFill BSM utilizing an arthroscopic / percutaneous approach as follows. Preoperatively, the subchondral bone defect is identified on a fat-suppressed MRI, and the approach and trajectory is planned based on defect location. Using intraoperative fluoroscopy, the bone defect is localized relative to MRI findings. The appropriate AccuPort® Delivery Cannula is drilled to the bone defect. AccuFill BSM is then injected into the subchondral bone defect. The AccuFill fills the defect and hardens within the subchondral bone defect, and is resorbed over time and replaced with new bone during the healing process.

It is recommended that a hip arthroscopy be performed prior to or after the Subchondroplasty procedure. In either case, the arthroscope should be placed into the joint after injection of AccuFill to check for possible material extravasation. Using standard arthroscopic surgery techniques, skin incisions are made for the insertion of arthroscopic instrumentation.

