10.7.1 Primary Endpoint

The primary endpoint is defined by the overall group mean improvement from baseline of the Modified Harris Hip Score at the two year time point. The safety of the system will be assessed by monitoring the frequency and incidence of adverse events. Relation of the events to implant (Accufill®), instrumentation (SCP® Surgical Instrumentation) and/or procedure should be specified.

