11.9 Surgical Reoperation or Revision

A reoperation of the index hip or revision of the SCP injection site may be performed at the discretion of the Investigator (e.g., due to progressive pain or disability, etc.). A reoperation is defined as any surgical procedure on the index hip. For the purposes of this protocol, a revision will be defined as any partial or total joint arthroplasty or any fusion, bone fixation, bone grafting, or bone substitute procedure in the study hip.

If the reoperation occurs due to an adverse event, the event should be documented on a Serious Adverse Event Form and an Exit Form completed, and the subject exited from the study.

In the event that a revision occurs (defined as any partial or total joint arthroplasty or any fusion, bone fixation, bone grafting, or bone substitute procedure in the index hip), the subject will be exited from the study. A Serious Adverse Event Form and an Exit Form will be completed.

Use of any postoperative injections into the index hip should be recorded on the Medication Form at the next questionnaire completion window.

12 Reporting

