13.2.3 Definitely Related

The serious adverse event is associated with the investigational device, comparator or with procedures beyond reasonable doubt.

Note: Complications caused by concomitant treatments not imposed by the clinical investigation plan are considered not related. Similarly, several routine diagnostic or patient management procedures are applied to patients regardless of the clinical investigation plan. If routine procedures are not imposed by the clinical investigation plan, complications caused by them are also considered not related.

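### Safety is measured by adverse-event incidence, yet the sponsor is sent only events the investigator judges related, and the status of arthroscopy complications is unclear

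*Combined protocol and SAP*

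**What the plan says.** Section 10.7.1, under the primary endpoint heading, states: "The safety of the system will be assessed by monitoring the frequency and incidence of adverse events". It adds that relation to implant, instrumentation "and/or procedure should be specified". Section 13.1.1 defines an adverse event regardless of its relation to the device.

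Section 12.4.9 narrows what is sent on: "only AEs which are possibly or definitely related to the device or procedure will be reported to the sponsor". The judgement lies with the site: "A causal relationship cannot be ruled out if, in the medical judgment of the Investigator, the effect follows a reasonable temporal association" with use of the device. The same section fixes the terms: "device implies the AccuFill Bone Substitute Material and procedure implies the Subchondroplasty Procedure".

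On arthroscopy, Section 7.1 says: "It is recommended that a hip arthroscopy be performed prior to or after the Subchondroplasty procedure". The note in Section 13.2.3 says: "Complications caused by concomitant treatments not imposed by the clinical investigation plan are considered not related".

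**The concern.** If safety is the incidence of adverse events, relatedness should describe each collected event. Section 12.4.9 makes it a condition for an event to reach the sponsor at all. In a single-arm study the person applying that condition is the treating investigator, and no comparator arm is subject to the same filter. Two things are at stake. First, the all-cause incidence that Section 10.7.1 appears to promise would be too low. Second, sites that resolve the conflicting instructions differently would report different numerators, which the descriptive summaries in Section 16.3 would then pool. Events never collected may not be recoverable later.

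**Working it through.** The documents state no adverse-event rate, no precision target and no safety sample size, so there is no plan figure to reproduce. The check is mainly a comparison of sections.

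**1. Instructions side by side**

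| Section | Instruction | Relatedness limit? |
|---|---|---|
| 10.7.1 | Frequency and incidence of adverse events; relation specified | No |
| 11.6 | In the immediate post-operative period, every adverse event and complication goes on the Adverse Event Form (with a pointer to 12.4.9) | No |
| 12.4.9 | Only possibly or definitely related events go to the sponsor | Yes |
| 13, opening | Adverse events go on the report form, and the form goes to the sponsor | No |
| 13.2 | Each event is classified, with None as one category | No |
| 13.3 | Sponsor reviews seriousness and relatedness of submitted events | Sees only what was submitted |

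A site that follows 11.6 and 13 submits everything. A site that follows 12.4.9 withholds what it calls unrelated. Section 11.6 points to 12.4.9, so it does not settle the matter.

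**2. Which events are exposed to the filter**

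Some events have a separate route with no relatedness test:
- Revisions (11.9, 12.4.2): "A Serious Adverse Event Form and an Exit Form will be completed".
- Reoperations due to an adverse event (11.9): a Serious Adverse Event Form.
- Deaths (12.4.5): an Adverse Event form.
- Intra-operative events (10.4, 11.5): recorded at surgery.

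The exposed events are the remainder: post-operative events, including serious ones, that lead to none of these and that the investigator judges unrelated.

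**3. How wide the filter is**

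The threshold is low. A reasonable temporal association is enough (12.4.9), even a remote possibility counts as possibly related (13.2), and unassessable cases default to possible (13.2.2). There are loose ends: 12.4.9 asks for a reasonable possibility while 13.2 admits a remote one; 13.2 announces four causality levels and lists three; and 12.4.9 limits the device to AccuFill although 10.7.1 also wants relation to the instrumentation.

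**4. Size, by assumption only**

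Reported incidence = true incidence × share of affected subjects whose event passes the filter. With n = 50:

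| Assumed true incidence | 90% pass | 75% pass | 50% pass | 25% pass |
|---|---|---|---|---|
| 20% (10 subjects) | 18% | 15% | 10% | 5% |
| 40% (20 subjects) | 36% | 30% | 20% | 10% |

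The 95% interval does not reveal the loss. The exact interval for 10/50 is 10.0% to 33.7%; for 5/50 it is 3.3% to 21.8%. With 0/50 the upper limit is 1 − 0.025^(1/50) = 7.1%, however many events were withheld.

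**5. Arthroscopy**

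Pointing towards procedure-related: 7.1 describes Subchondroplasty as done through an arthroscopic or percutaneous approach and says the arthroscope should enter the joint after injection; 6.4.1 lists the risks of hip arthroscopy as the surgical risks. Pointing the other way: 7.1 only recommends arthroscopy, 12.4.9 names only the Subchondroplasty Procedure, and the 13.2.3 note removes complications of concomitant treatments that the plan does not impose. The text does not settle it.

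If a site did exclude such events, expected number missed = 50 × share having arthroscopy × complication rate, and the chance of missing at least one = 1 − (1 − share × rate)^50. All inputs except 50 are assumptions:

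| Assumed complication rate | All have arthroscopy | Half have arthroscopy |
|---|---|---|
| 2% | 1.0 missed (64%) | 0.5 (39%) |
| 5% | 2.5 (92%) | 1.25 (72%) |
| 10% | 5.0 (99%) | 2.5 (92%) |

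**The case against.** Related-only reporting looks deliberate in a post-market study that rates the physical risk of participation as minimal. The formal primary endpoint is the change in Modified Harris Hip Score, and safety has no hypothesis. If related events were always the target, the filter loses nothing except through misjudged relatedness. The low threshold means peri-operative events are the least likely to be withheld. Monitors also have access to hospital notes (Section 14), and audits cover medical records (Section 17).

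Much of this stands. It rules out any claim that a particular share, such as half, of events would be lost. It also answers the reading that a hip replacement could vanish because 12.4.9 has it recorded under a diagnosis such as osteoarthritis: 11.9 treats any arthroplasty of the study hip as a revision and requires a serious-event form without asking about relatedness, and the 12.4.9 example is about what diagnosis to write once an event is being reported.

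Two things do not stand. Section 10.7.1 does not say that only related events count, and asking for relation to be specified implies that it varies among the events counted. And monitoring is not a systematic remedy: Section 14 says the monitor may check entries against source, looking mainly at the operative form, while 13.3 reviews only what was submitted.

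**Conclusion.** The conflict between the safety measure and the reporting rule is real and should be resolved. If 12.4.9 is followed as written, all-cause adverse-event incidence is biased downwards, except for revisions, reoperations due to an adverse event, deaths and intra-operative events. The direction rests on reading 10.7.1 as all adverse events, which is what its wording and the definition in 13.1.1 say. The documents do not allow the amount to be calculated; the tables above show only how it would scale under assumed rates.

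A reader might infer that complications of the recommended arthroscopy are ruled not related. The documents do not support that: the note in 13.2.3 does not name arthroscopy, and 6.4.1 and 7.1 support treating it as part of the procedure. What is supported is that the classification is unclear, so a site could exclude these events as not imposed by the plan.

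**What to change.** - In 12.4.9, require submission of all serious adverse events and all index-hip or peri-operative adverse events, whatever the attribution.
- On CRF 11, record relation to AccuFill, instrumentation, the Subchondroplasty Procedure and concomitant procedures as separate fields.
- In 16.3, report both total and related incidence for those events.
- In 13.2.3, state how events from arthroscopy in the same session are classified.
- Reconcile 10.7.1, 11.6, 11.9, 12.4.2, 12.4.9, the opening of 13, 13.2, 13.2.3 and 13.3, including the possibility threshold and the number of causality levels.
- If only related events are intended, say so in 10.7.1 and label the result as related adverse-event incidence.

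The cost is an amendment to the reporting and CRF wording, some additional adverse-event forms in about 50 subjects, and higher reported adverse-event rates. Events that sites have already withheld may be only partly recoverable from source records.

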13.1 Classification of the Event

13.1.1 Adverse Event (AE)

An adverse event is any untoward medical occurrence, unintended disease or injury, or untoward clinical signs (including abnormal laboratory findings) in subjects, users or other persons, whether or not related to the investigational medical device and whether anticipated

or unanticipated.

Note 1: This definition includes events related to the investigational medical device or the comparator.

Note 2: This definition includes events related to the procedures involved.

Note 3: For users or other persons, this definition is restricted to events related to investigational medical devices or comparators.

13.1.2 Serious Adverse Event (SAE)

A Serious Adverse Event is an adverse event that led to any of the following:

- death,
- serious deterioration in the health of the subject, users or other persons as defined by one or more of the following:
 - a life-threatening illness or injury, or
 - a permanent impairment of a body structure or a body function including chronic diseases, or
 - in-patient or prolonged hospitalization, or
 - medical or surgical intervention to prevent life-threatening illness or injury or permanent impairment to a body structure or a body function, led to fetal distress, fetal death or a congenital abnormality or birth defect including physical or mental impairment.

Note: Planned hospitalization for a pre-existing condition, or a procedure required by the protocol, without serious deterioration in health, is not considered a serious adverse event.

13.1.3 Serious Health Threat

Signal from any adverse event or device deficiency that indicates an imminent risk of death or a serious deterioration in the health of subjects, users or other persons, and that requires prompt remedial action for other subjects, users or other persons.

Note 1: This would include events that are of significant and unexpected nature such that they become alarming as a potential serious health hazard or possibly of multiple deaths occurring at short intervals.

13.1.4 Adverse Device Effect (ADE)

An Adverse Device Effect is an adverse event related to the use of an investigational medical device.

Note 1: This definition includes adverse events resulting from insufficient or inadequate instructions for use, deployment implantation, installation, or operation, or any malfunction of the medical device.

Note 2: This definition includes any event resulting from use error or from intentional misuse

of the medical device.

13.1.5 Serious Adverse Device Effect (SADE)

A Serious Adverse Device Effect is an adverse device effect that has resulted in any of the consequences characteristic of a serious adverse event.

13.1.6 Unanticipated Serious Adverse Device Effect (USADE)

An unanticipated adverse device effect is a serious adverse device effect which by its nature, incidence, severity or outcome has not been identified in the current risk assessment.

Note 1: Anticipated serious adverse device effect (ASADE) is an effect which by nature, incidence, severity or outcome has been identified in the risk assessment.

13.1.7 Device Deficiency (DD)

A Device Deficiency is defined as an inadequacy of a medical device with respect to its identity, quality, durability, reliability, usability, safety or performance.

Note: Device Deficiencies include malfunctions, use errors, and inadequacy in the information supplied by the manufacturer including labeling.

It is important to document in the study also all device deficiencies that could have led to a medical occurrence but did not lead to an adverse event.

13.2 Causality Assessment (Relation to Device)

The relationship between the use of the medical device (including the medical - surgical procedure) and the occurrence of each adverse event shall be assessed and categorized.

During causality assessment activity, clinical judgement shall be used and the relevant documents, such as the Investigator's Brochure, the Clinical Investigation Plan or the Risk Analysis Report shall be consulted, as all the foreseeable serious adverse events and the potential risks are listed and assessed there. The presence of confounding factors, such as concomitant medication/treatment, the natural history of the underlying disease, other concurrent illness or risk factors shall also be considered.

Each adverse event will be classified according to four different levels of causality:

- None (definitely not related)
- Possibly Related (remote possibility, possibly, or probably related)
- Definitely related

The sponsor and the investigators will use the following definitions to assess the relationship of the adverse event to the investigational device, the comparator or the investigation procedure.

13.2.1 None

Relationship to the device, comparator or procedures can be excluded when the event has

no temporal relationship with the use of the investigational device, or the procedures related to application of the investigational device.

13.2.2 Possibly Related (Uncertain)

The relationship with the use of the investigational device or comparator, or the relationship with procedures, is weak but cannot be ruled out completely. Alternative causes are also possible (e.g. an underlying or concurrent illness/ clinical condition or/and an effect of another device, drug or treatment). Cases where relatedness cannot be assessed, or no information has been obtained should also be classified as possible.

13.2.3 Definitely Related

The serious adverse event is associated with the investigational device, comparator or with procedures beyond reasonable doubt.

Note: Complications caused by concomitant treatments not imposed by the clinical investigation plan are considered not related. Similarly, several routine diagnostic or patient management procedures are applied to patients regardless of the clinical investigation plan. If routine procedures are not imposed by the clinical investigation plan, complications caused by them are also considered not related.

13.3 Review of Reported Events

The Sponsor will review the investigator's assessment of all reported events submitted to determine and document in writing their seriousness and relationship to the study device and related procedures required by this protocol. In case of disagreement, the sponsor will consult the investigator for clarification and correction if required. If the disagreement cannot be resolved, the sponsor shall communicate both opinions to the Post Market Surveillance team for further investigation and required reporting if applicable.

13.4 Intensity of Symptoms

13.4.1 Mild

The subject is aware of the sign or symptom, but finds it easily tolerated. The event is of little concern to the subject and/or little clinical significance. The event is not expected to have any effect on the subject's overall health or well-being.

13.4.2 Moderate

The subject has discomfort enough to cause interference with or a change in usual activities. The event is of some concern to the subject's health or well-being and may require medical intervention and/or close follow-up.

13.4.3 Severe

The event interferes considerable with the subject's usual activities. The event is of definite concern to the subject and/or poses substantial risk to the subject's health or well-being. The event is likely to require medical intervention and/or close follow-up and may be incapacitating or life threatening. Hospitalization and treatment may be required.

Note: The term “severe” refers to the intensity of the event and can be used with any event, without regard to whether or not it meets the criteria for being classified as “serious” or “unanticipated”. For example, a subject can have a severe headache, but it is not a serious event.

